4.6.3.1 Primary Endpoints

PFS-6 using the RANO criteria (see Section 18.2) will be used as primary endpoints.

4.6.3.2.Secondary Endpoints

- Safety of the combination of SGT-53 and Temozolomide.
- PFS, OS
- Anti-tumor activity of the combination of SGT-53 and Temozolomide based upon the RANO criteria.
- The induction of apoptosis by SGT-53 in the tumor (optional procedure).
- Nanoparticle delivery (optional procedure)

4.6.4. Statistical hypothesis and sample size:

A total of 26 patients will be enrolled. A maximum of 6 patients will be enrolled to participate in the optional surgical resection for tumor analysis.

Patients who have received at least one dose of study drug will be considered evaluable for safety and toxicity endpoints. Patients who require a dose interruption or reduction during the initial cycle will remain evaluable for toxicities if the reduction or interruption is due to a DLT. Patients who do not complete one cycle of treatment but do not have a DLT may be replaced as described in more detail in Section 9.6.

The primary endpoint for the trial is PFS6. Progression-free survival will be defined as the time from study enrollment until the time of first occurrence of disease progression, relapse, or death due to disease.

The analysis of the biological correlate data in patients with surgical resection for tumor analysis has the overall goal of providing an increased understanding of the ability of SGT-53 to cross the Blood-brain Barrier and be delivered into tumor cells in the brain. As such, the objective of the tumor analysis is qualitative rather than quantitative. It should be noted that in the Phase I dose escalation trial of SGT-53, the presence of the exogenous wtp53 delivered by SGT-53 was found to be present in the tumors in a DNA dose dependent manner. Moreover, even the lowest dose of SGT-53 (0.6mg DNA/infusion) was not only found to be present in the tumors of the patients, but to have some anti-tumor effect. A DNA dose 6-fold higher (3.6mg DNA/infusion) is being used in this trial.

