In patients with refractory anaplastic astrocytoma, the most frequently occurring adverse reactions were nausea, vomiting, headache, and fatigue. The adverse reactions were usually NCI Common Toxicity Criteria (CTC) Grade 1 or 2 (mild to moderate in severity) and were self-limiting, with nausea and vomiting readily controlled with antiemetics. The incidence of severe nausea and vomiting (CTC Grade 3 or 4) was 10% and 6%, respectively. Myelosuppression (thrombocytopenia and neutropenia) was the dose limiting adverse reaction. It usually occurred within the first few cycles of therapy and was not cumulative. Myelosuppression occurred late in the treatment cycle and returned to normal, on average, within 14 days of nadir counts. The median nadirs occurred at 26 days for platelets (range: 21-40 days) and 28 days for neutrophils (range: 1-44 days). Only 14% (22/158) of patients had a neutrophil nadir and 20% (32/158) of patients had a platelet nadir, which may have delayed the start of the next cycle. Less than 10%

of patients required hospitalization, blood transfusion, or discontinuation of therapy due to myelosuppression.

In clinical trial experience with 110 to 111 women and 169 to 174 men (depending on measurements), there were higher rates of Grade 4 neutropenia (ANC <500 cells/ μ L) and thrombocytopenia (<20,000 cells/ μ L) in women than men in the first cycle of therapy (12% vs. 5% and 9% vs. 3%, respectively).

In the entire safety database for which hematologic data exist (N=932), 7% (4/61) and 9.5% (6/63) of patients over age 70 experienced Grade 4 neutropenia or thrombocytopenia in the first cycle, respectively. For patients less than or equal to age 70, 7% (62/871) and 5.5% (48/879) experienced Grade 4 neutropenia or thrombocytopenia in the first cycle, respectively. Pancytopenia, leukopenia, and anemia have also been reported.

Contraindication:

Temozolomide is contraindicated in patients who have a history of hypersensitivity reaction (such as urticaria, allergic reaction including anaphylaxis, toxic epidermal necrolysis, and Stevens-Johnson syndrome) to any of its components. TEMODAR is also contraindicated in patients who have a history of hypersensitivity to DTIC, since both drugs are metabolized to 5-(3-methyltriazen-1-yl)-imidazole-4-carboxamide (MTIC).

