9.7.1. SGT-53 and/or Temozolomide

Table 9.7.1. reviews management of **non-hematologic** toxicities as they pertain to both study agents SGT-53 and/or Temozolomide.

Toxicity	Grade 1	Grade 2	Grade 3	Grade 4
Hyperbilirubin-	Continue both	Hold both until	Discontinue	Discontinue
emia	at same dose	grade 1 or less	TMZ, hold	TMZ, hold
Ciliu		in 2 weeks	SGT-53 until	SGT-53
		in 2 woods	grade 1 or less	until grade 1
			(up to 2	or less (up to
			weeks)*	2 weeks)*
AST &/or ALT	Continue both	Hold both until	Discontinue	Discontinue
	at same dose	grade 1 or less	TMZ, hold	TMZ, hold
		in 2 weeks	SGT-53 until	SGT-53
			grade 1 or less	until grade 1
			(up to 2	or less (up to
			weeks)*	2 weeks)*
Dyspnea not	Continue both	Hold both until	Discontinue	Discontinue
associated with	at same dose	grade 1 or less	TMZ, hold	TMZ, hold
infusion		in 2 weeks	SGT-53 until	SGT-53
			grade 1 or less	until grade 1
			(up to 2	or less (up to
			weeks)*	2 weeks)*
DIC	Continue both	Hold both until	Discontinue	Discontinue
	at same dose	grade 1 or less	TMZ, hold	TMZ, hold
		in 2 weeks	SGT-53 until	SGT-53
			grade 1 or less	until grade 1
			(up to 2	or less (up to
			weeks)*	2 weeks)*
Fatigue	Continue both	Continue both	Hold both until	Discontinue
	at same dose	at same dose	grade 1 or less	both
			in 2 weeks	
Infusion	May	May		
reaction	rechallenge	rechallenge		
	after 1 st event,	after 1 st event,	Discontinue inciting agent**	
	if resolves in 2	if resolves in 2		
	h**	h**		
Hypotension	See Section	See Section	See Section 9.3.2	•
during infusion	9.3.2.	9.3.2.		

Other non-	Continue both	Hold both until	Hold both until	Discontinue
hemetoxicity***	at same dose	grade 1 or less	grade 1 or less	both
		in 2 weeks	in 2 weeks	

^{*}If toxicity reduces to grade 1 or less in 2 weeks, patient may continue SGT-53 until end of cycle at discretion of investigator.

***Other non-heme toxicity refers to any non-heme toxicity at least possibly related to SGT-53, or temozolomide with the exception of alopecia, inadequately treated nausea, vomiting, diarrhea, or fever, chills or hypotension which respond promptly to treatment and lasts less than 24 hours.

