For grade 2 events of increased bilirubin, AST, ALT, dyspnea, or DIC, the dose of SGT-53 and Temozolomide can be held for up to two weeks. If the grade 2 event reduces at least to grade 1 within two weeks, then infusion of SGT-53 and Temozolomide can resume at the same dose per calendar at incident week + 1-2 weeks (i.e., treatment would be made up and moved 1-2 weeks later).

For non-hematological events other than increased bilirubin, AST, ALT, dyspnea, or DIC, participants who develop a > or = grade 2 toxicity (except for alopecia, fever, chills or hypotension that respond to treatment) or grade 3 fatigue will discontinue twice-weekly infusions until the toxicity level reduces to at least grade 1. Infusions will be held for one week intervals, and infusions that are withheld will be made-up (i.e. moved 1-2 weeks later). If the toxicity does not resolve within two weeks, study drug will be discontinued.

A minimum of 2-week rest period will be required if there is grade III or greater non-hematologic toxicity related to SGT-53/Temozolomide that cannot be controlled with supportive medications/measures. After the minimum 2-week rest period and the toxicity has resolved to a grade II or better, the patient will resume taking the drug at a reduced dose level as shown in Table 9.7.2b below.

Subjects who receive less than four of twelve of the intended drug infusions, due to experiencing these grade 2 events that have not resolved as described above, and that are determined by the PI to be at least probably related to SGT-53, will be considered to have experienced a DLT.

Patients forced to discontinue temozolomide due to a temozolomide-related toxicity (e.g., grade 3, 4 hypersensitivity) will be removed from the study.

^{**}Note that infusion reactions are discussed in detail in Section 9.3.2.

9.7.2. Temozolomide

Table 9.7.2a. reviews management of hematologic toxicities associated with Temozolomide treatment. Note that there are no dose adjustments for anemia.

	Grade 1	Grade 2	Grade 3 or Grade 4
Neutropenia	< LLN to	<1500 to	Grade 3: <1000 to 500/mm ³
	$1500/\text{mm}^3$	$1000/\text{mm}^3$	Grade 4: <500/mm ³
			If resolves to grade ≤ 2 within 14
	Proceed at	Proceed at	days, rechallenge at same dose of
	current dose	current dose	SGT-53, and reduce dose of TMZ
			in increments after each event
			according to Table 9.7.2b below,
			i.e. in Cycle 1reduce to 100
			mg/m ² after the first event, in
			Cycle 2 reduce to 150 mg/m2

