10.2. Evaluation During Study

The starting dose of SGT-53 will be 3.6 mg of DNA. If necessary, dose de-escalation for SGT-53 will proceed according to the dose de-escalation scheme in Table 9.7.3 above. Assessment of DLTs will be made based on the first cycle (4 weeks of treatment). At the end of the first cycle, if no DLT are observed, additional patients may be enrolled and treated simultaneously. If the first patient experiences a DLT in the first cycle (4 weeks), then only one additional patient will be enrolled and evaluated for DLT. If the second patient does not experience DLT in the first cycle (4 weeks), then additional patients may be enrolled simultaneously.

10.2.1. Patients with Optional Surgical Resection for Tumor Analysis:

Beginning 5 days prior to scheduled surgical resection of their recurrent glioblastoma, patients will initiate 3.6mg DNA dosing/infusion with SGT. Dosing will continue through the day before surgery.

• One portion of the surgical section will be saline rinsed and flash frozen for measurement of exogenous wt p53 in tumor tissue, one portion will be immediately formalin-fixed for evaluation of PD biomarkers of activity of SGT-53 including but not limited to Annexin V and TUNEL staining. In addition, one portion of fresh tissue will be used for flow cytometry and/or immunohistochemistry analysis to determine the level of apoptosis in Cancer Stem Cells (CSC) and bulk tumor cells. Any remaining tumor tissue from an earlier procedure will be collected and stored in a research tissue bank at Georgetown University or the clinical site.

Following surgery, an MRI scan should be done no later than 72 hours from the time of surgery.

Following recovery from surgical resection (POD ~14-21), patients will restart SGT-53 and TMZ on the morning of Cycle 1 Day 1 (C1D1). Each cycle will consist of 28 days. Patients will return to the clinic for twice weekly (every 3rd or 4th day) infusions of SGT-53 for three weeks (see treatment schedule diagram in section 9.1.1). Temozolomide will be taken daily by mouth daily on days 9-13 of each cycle. During week 4 of each cycle the patient will not receive any treatments. Patients will return to the clinic on Day 29 (C2D1) and Day 57 (C3D1) for evaluation. If the drug has been well tolerated, continued dosing will be permitted even if they appear to be progressing.

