Patients will return to clinic at least weekly for assessments (until the last week of protocol therapy). Refer to the Study Calendar, Appendix 18, for evaluations to be completed during each clinic visit. Each clinic visit will include: assessment of vital signs (blood pressure, pulse and temperature). The following will be performed only on a weekly basis (usually on the first visit of each week) unless clinically significant values were obtained at the previous visit: physical exam; assessment of the ECOG/ Karnofsky Performance Status; assessment of concomitant medications; assessment of adverse events; completion of a serum chemistry panel; completion of a CBC with differential. At the beginning of every cycle a urinalysis panel will be completed. A 12-lead ECG and echocardiogram will be performed at baseline. Additional ECGs/ echocardiograms should be obtained on any patient who demonstrates signs or symptoms of myocardial degeneration. Additionally a 12-lead ECG will be performed 2 hours and 24 hours after the first infusion of SGT-53. A 12-lead ECG will be performed weekly (2 hours postinfusion) during the first 2 weeks of cycle 1, and at the End Of Treatment (EOT) visit. If these patients receive additional rounds of SGT-53/Temozolomide a 12-lead ECG will only be performed as necessary and at the EOT visit.

The first two subjects enrolled in this trial under the current protocol will be monitored for PT/PTT, D-dimer and LDH at baseline/screening; in cycle 1 ~20 hours after the first infusion (during the 23 observation period), and weekly during cycle 1, and once in two weeks during cycles 2 and 3 and at the exit visit. If these patients receive additional rounds of SGT-53/Temozolomide PT/PTT, D-dimer and LDH will be monitored once in two weeks during cycle 1 and monthly in cycle 2 and beyond.

Subsequent subjects will be monitored for PT/PTT, D-dimer and LDH at:

- (i) baseline/screening;
- (ii) in cycle 1 (a) ~20 hours after the first infusion (during the 23 observation period)
- (iii) at the exit visit.

Patients who are responding to treatment (at least stable disease by RANO) may receive three additional cycle of SGT-53/temozolomide therapy at investigator's discretion. Alternatively, they may continue on Temozolomide alone at investigator's discretion.

10.2.4. End of Treatment Evaluations (Day 85, at the end of Cycle 6 if the patient received cycles 4-6, or for premature withdrawal/study drug discontinuation)

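### The only DLT criterion counts infusions out of twelve, but DLTs are assessed over a six-infusion cycle; on schedule it cannot capture events starting after day 11, cytopenias, or events that resolve within two weeks

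*Combined protocol and SAP*

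**What the plan says.** Section 10.2 fixes the DLT window as the first 28-day cycle and makes the result a gate: "At the end of the first cycle, if no DLT are observed, additional patients may be enrolled and treated simultaneously". If the first patient has a DLT, only one more patient is enrolled and evaluated before enrolment opens up.

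Section 4.6.4 uses the term twice. A patient whose dose is cut or interrupted in the initial cycle "will remain evaluable for toxicities if the reduction or interruption is due to a DLT". A patient who does not complete one cycle and has had no DLT may be replaced.

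For the definition, 8.1 and 10.5 send the reader to 9.7, while 11.7, whose title is the definition of DLT, sends the reader to 9.4. The one sentence that states when a patient has a DLT is in 9.7.1: "Subjects who receive less than four of twelve of the intended drug infusions, due to experiencing these grade 2 events that have not resolved" as set out earlier in that section, and "that are determined by the PI to be at least probably related to SGT-53, will be considered to have experienced a DLT".

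Sections 5 and 9 give SGT-53 on days 1, 4, 8, 11, 15 and 18 of each cycle and temozolomide (TMZ) on days 9 to 13, for three cycles, with three further cycles possible.

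**The concern.** A gate on early enrolment works only if its trigger responds to the toxicity it is meant to catch. Here the trigger counts infusions received, over a denominator that is not the one for the assessment window. Once the fourth infusion has been given, no later event can satisfy it, however severe. It also leaves out the blood-count toxicity for which 9.7.2 and 9.7.3 have detailed rules.

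At stake is whether serious toxicity in the first patient obliges the trial to slow down, and whether that patient is kept as evaluable or treated as replaceable. The question is not idle. The human experience described in 4.4.1 and 4.4.2 is SGT-53 alone at up to 3.6 mg and SGT-53 at 2.4 mg with docetaxel, not 3.6 mg with TMZ.

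**Working it through.** **Inputs.** Infusion days 1, 4, 8, 11, 15, 18 and TMZ days 9 to 13 (sections 5 and 9). DLT window days 1 to 28 (10.2). Criterion: fewer than 4 of 12 infusions (9.7.1).

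**1. Can twelve be reproduced?** Intended infusions = 6 × cycles, plus 2 if the optional pre-surgery infusions are counted.

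| Cycles | Infusions | With pre-surgery infusions |
|---|---|---|
| 1 | 6 | 8 |
| 2 | 12 | 14 |
| 3 | 18 | 20 |
| 6 | 36 | 38 |

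Only two cycles give twelve, and no section uses two cycles as the DLT window.

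**2. Which onset days can meet the criterion?** For an event starting on day d that stops dosing, count the scheduled infusion days before d.

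| Onset day | Infusions already given | Fewer than 4? |
|---|---|---|
| 1 | 0 | yes |
| 2–4 | 1 | yes |
| 5–8 | 2 | yes |
| 9–11 | 3 | yes |
| 12–15 | 4 | no |
| 16–18 | 5 | no |
| 19–28 | 6 | no |

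On schedule, the last qualifying onset is day 11, before that day's infusion. Section 9.1.1 allows other schedules. Infusions on days 1, 5, 8, 12 move the cut-off to day 12, and infusions on days 1, 5, 9, 13 move it to day 13. If the two pre-surgery infusions count, the cut-off falls to day 4.

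**3. Which events does the sentence refer back to?** The preceding paragraphs of 9.7.1 deal with bilirubin, AST, ALT, dyspnoea and DIC at grade 2, and then with other non-haematologic events. Neutropenia and thrombocytopenia are in Tables 9.7.2a and 9.7.3, which hold, reduce or withdraw treatment without mentioning DLT.

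**4. What if the event resolves?** The sentence requires non-resolution. In the paragraphs on held doses, an event that falls to grade 1 within two weeks leads to resumed and made-up infusions, so it does not qualify.

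**5. Does another section fill the gap?** Section 9.4, where 11.7 points, lists reasons for withdrawal and for holding doses but never uses the term DLT. The rest of 9.7 adds no DLT wording. Sections 4.6.4 and 10.2 use the term without defining it, although the mention of dose reduction in 4.6.4 suggests that a wider meaning was intended.

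**6. Worked case.** A drug-related grade 4 non-haematologic event, of the kind Table 9.7.1 classes as other, starts on day 14. Infusions received = 4 (days 1, 4, 8, 11); TMZ doses received = 5 (days 9 to 13). Since 4 is not fewer than 4, the criterion is not met. Table 9.7.1 stops both drugs, so the cycle is not completed. With no DLT recorded, 10.2 requires no pause and 4.6.4 allows replacement.

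**7. Would changing twelve to six be enough?** With the rule written as fewer than k of 6, the last qualifying onset is the day of the k-th infusion: k = 2, day 4; k = 3, day 8; k = 4, day 11; k = 5, day 15; k = 6, day 18. Even the loosest version cannot reach days 19 to 28. Scaling 4/12 to 2/6 narrows the window to onsets by day 4.

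**The case against.** The strongest reply is that 9.7.1 states a sufficient condition. It says that such patients count as having a DLT, not that only they do. That stands. A reader might infer that the plan declares the day-14 case free of DLT; it does not. The case is simply not captured by any stated criterion. The practical result is similar, because 10.2 and 4.6.4 act on whether a DLT has been observed and nothing tells the investigator to record one.

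The second reply is that other safeguards remain, and this also stands. Grade 4 events must be reported as serious (11.4), the sponsor is told within 24 hours and the monitoring committee receives the report (11.16). The DSMB and IRB can stop accrual (section 14), and the sponsor can stop the study (15.1). Replacement is decided by the Safety Monitoring Committee (9.5). These powers are discretionary, whereas 10.2 was written as a required step. The statement in 9.6 that its parameters are only a guide concerns dose modification and supplies no DLT definition.

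Two further readings are tempting but unsupported. A reader might turn days 12 to 28 into a share of the toxicity missed. Days are not risk: 11.6 places the known fever and hypotension after the first infusion, within days 1 to 11. A reader might also infer from the TMZ nadir times in 7.1 that a four-week window is itself too short. Those figures come from refractory anaplastic astrocytoma, the day they are counted from is not stated, and the neutrophil range begins at day 1.

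**Conclusion.** The DLT rule is wrong as written and should be fixed. Its denominator of twelve matches neither the 6 infusions in the assessment window nor the 18 in three cycles. On schedule it cannot capture events starting after day 11, neutropenia or thrombocytopenia, or events that resolve within two weeks. The cross-references disagree, and the one in 11.7 leads to a section with no DLT wording.

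The rule is not empty: an unresolved non-haematologic event starting by day 11 and at least probably related to SGT-53 can still meet it. Nor does it force an unsafe decision; it fails to require a pause. The enrolment gate covers only the first one or two patients, and the Simon rule for PFS6 does not use DLTs directly.

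The day-11 cut-off assumes dosing on the stated schedule; permitted alternatives move it by a day or two. The enrolment consequence assumes that the gate is still to be applied under Amendment 6, which the protocol does not show. If it has already been passed, the effect on replacement and evaluability in 4.6.4 and the broken cross-reference remain.

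**What to change.** Replace the sentence in 9.7.1 with one cycle-1 DLT definition that applies whatever the number of infusions received. It should cover:

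- non-haematologic events of grade 3 or higher related to study drug, keeping the exceptions already in the footnote to Table 9.7.1 ("with the exception of alopecia, inadequately treated nausea, vomiting, diarrhea, or fever, chills or hypotension which respond promptly to treatment" within the time limit given there);
- grade 4 neutropenia or thrombocytopenia, as graded in Table 9.7.2a.

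These thresholds are proposals, and the sponsor and DSMB should confirm the exact ones. If a missed-infusion limb is kept for unresolved grade 2 events, its denominator should be the 6 cycle-1 infusions and it should only supplement the definition. Sections 8.1, 10.5 and 11.7 should all point to the new text.

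The direct cost is amendment wording, with no extra patients, visits or procedures required by the definition itself. There are two indirect costs. A broader DLT may trigger the one-additional-patient, 4-week step in 10.2 more often, and fewer early drop-outs will be replaceable under 4.6.4. Section 10.2 also does not say what happens if the second patient has a DLT; since that becomes more likely, the same amendment should settle it.

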			after the first event, if recurs
			reduce to 100 mg/m ² etc
			If recurs at lowest dose of TMZ
			(100 mg/m ² or less), withdraw
			from study. If at any time it does
			not resolve within 14 days,
Tr1 1	ZUNA	<75 000 to	withdraw from study.
Thrombo-	<lln td="" to<=""><75,000 to	Grade 3: <50,000 to 25,000/mm³	</lln>	<75,000 to	Grade 3: <50,000 to 25,000/mm ³
cytopenia	$75,000/\text{mm}^3$	50,000/mm ³	Grade 4: <25,000/mm ³
	Proceed at	Proceed at	If resolves to grade ≤ 2 within 14 days, rechallenge at same dose of
	current dose	current dose	SGT-53, and reduce dose of TMZ
	current dosc	current dosc	in increments after each event
			according to Table 9.7.2b below,
			i.e.in Cycle 1 reduce to 100
			mg/m^2 after the first event, in
			Cycle 2 reduce to 150 mg/m ² after
			the first event, if recurs reduce to
			100 mg/m ² etc
			If recurs at lowest dose of TMZ
			(100 mg/m ² or less), withdraw
			` '
			not resolve within 14 days,
			withdraw from study.
			(100 mg/m ² or less), withdraw from study. If at any time it does not resolve within 14 days,

Table 9.7.2.b Dose de-escalation for TMZ:

Treatment Cycle	Agent	Schedule	Level	Level	Level
			0 (Target Dose)	-1	-2
Cycle 1	TMZ	Days 9-13	150 mg/m^2	100mg/m^2	
Cycle 2 onwards		Days 9-13	200 mg/m ²	150 mg/m ²	100 mg/m^2

In the event of grade III or higher toxicity associated with TMZ after cycle 1, treatment will be interrupted and patient monitored for resolution of toxicity, with subsequent reinitiation of treatment. TMZ dosing will resume after complete resolution of toxicities to Grade II or less.

The dose of Temozolomide will only be escalated to 200 mg/m2 if the patient meets the following criteria: If the CTC nonhematologic toxicity for Cycle 1 is \leq Grade 2 (except for alopecia, nausea, and vomiting, diarrhea, or fever, chills or hypotension which respond promptly to treatment and lasts less than 24 hours), absolute neutrophil count (ANC) is \geq 1,500/mm³, and the platelet count is \geq 100,000/mm³. The dose remains at 200 mg/m2 per day for the first 5 days of each subsequent cycle except if toxicity occurs. If the dose was not escalated at Cycle 2, escalation should not be done in subsequent cycles.

If more than a 2 week delay is required to meet hematologic parameters for treatment, the patient must be removed from study and replaced.

9.7.3. Dose de-escalation for SGT-53:

Permitted dose modifications for SGT-53

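### Tables 9.7.2a and 9.7.2.b set the first temozolomide reduction by cycle, not by the preceding dose, so some patients on 150 mg/m2 are told to reduce to 150 mg/m2

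*Combined protocol and SAP*

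**What the plan says.** Temozolomide is given on days 9-13 of each 28-day cycle, at 150 mg/m2 in Cycle 1 and 200 mg/m2 from Cycle 2 if criteria are met (protocol Sections 4.6, 5 and 9).

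- **Reduction rule.** Table 9.7.2a covers grade 3-4 neutropenia and thrombocytopenia that recover to grade 2 or less within 14 days. In both rows the dose comes down in increments after each event. For Cycle 1 the thrombocytopenia row has "i.e.in Cycle 1 reduce to 100" mg/m2. For a first event in Cycle 2 the rule is "Cycle 2 reduce to 150 mg/m2", then 100 mg/m2 if it recurs. Recurrence at the lowest dose means withdrawal.
- **Dose levels.** Table 9.7.2.b is also arranged by cycle. Cycle 1 goes 150, 100; Cycle 2 onwards goes 200, 150, 100.
- **Escalation.** "The dose of Temozolomide will only be escalated to 200 mg/m2 if the patient meets the following criteria": Cycle 1 non-hematologic toxicity no worse than grade 2 (with listed exceptions), ANC at least 1,500/mm³ and platelets at least 100,000/mm³. A patient who misses this stays at 150 mg/m2, and "If the dose was not escalated at Cycle 2, escalation should not be done in subsequent cycles".
- **Nadir timing.** Section 7.1 states: "The median nadirs occurred at 26 days for platelets (range: 21-40 days) and 28 days for neutrophils (range: 1-44 days".

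**The concern.** A reduction rule should start from the dose that caused the toxicity. This one starts from the cycle number. That is harmless when every patient in Cycle 2 has received 200 mg/m2, but Section 9.7.2 itself provides for patients who have not.

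For them the printed step repeats the dose just given. The path to withdrawal becomes 150, 150, 100, out, where one step per event would give 150, 100, out. The patient can have one more severe cytopenia before withdrawal, at a dose 50% above 100 mg/m2. This is a matter of patient safety and of two sites applying one rule in the same way. No effect on the primary endpoint is shown.

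**Working it through.** **1. The printed step.** In Table 9.7.2.b, row Cycle 2 onwards, Level -1 is 150 mg/m2. This matches Table 9.7.2a.

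**2. Patient not escalated at Cycle 2.** The dose in Cycle 2 is 150 mg/m2. A first grade 3-4 cytopenia in Cycle 2 or later falls under the Cycle 2 onwards row, whether the event is assigned by calendar or by the course that caused it. Printed step: 150 to 150, a cut of 0%. One true step would be 150 to 100, a cut of 50/150 = 33%. No row of Table 9.7.2.b for Cycle 2 onwards starts at 150.

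**3. Event from the Cycle 1 course first seen early in Cycle 2.** Temozolomide starts on study day 9 and ends on day 13. Cycle 2 day 1 (C2D1) is day 29, and Cycle 2 temozolomide starts on day 37 (C2D9). Section 7.1 does not state where its nadir days start, so three counts are shown:

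| Count | Platelet median (26 d) | Neutrophil median (28 d) |
|---|---|---|
| First dose is day 1 | 9 + 25 = 34, C2D6 | 9 + 27 = 36, C2D8 |
| Days after first dose | 9 + 26 = 35, C2D7 | 9 + 28 = 37, C2D9 |
| Days after last dose | 13 + 26 = 39, C2D11 | 13 + 28 = 41, C2D13 |

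With dosing on days 1-5, first dose as day 1, the medians would be C1D26 and C1D28, inside Cycle 1. On days 9-13 both fall in Cycle 2 on every count. But the printed 150 mg/m2 equals the only dose so far given only up to C2D8. That window contains both medians on the first count, the platelet median alone on the second, and neither on the third. The study calendar (Section 18.1) schedules blood counts on C2D1 and C2D8, so such an event can be seen there.

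**4. How many patients.** Section 7.1 gives first-cycle grade 4 rates. For patients aged 70 or younger: "7% (62/871) and 5.5% (48/879) experienced Grade 4 neutropenia or thrombocytopenia in the first cycle". For those over 70: 4/61 and 6/63.

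- Neutropenia: (62 + 4)/(871 + 61) = 66/932 = 7.1%; × 26 = 1.84 patients.
- Thrombocytopenia: (48 + 6)/(879 + 63) = 54/942 = 5.7%; × 26 = 1.49 patients.

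First dose as day 1, and at least half of each nadir type seen on C2D1-D8:

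- Low, half of each type, full overlap: max(1.84/2, 1.49/2) = max(0.92, 0.75) = 0.9.
- High, all of both types, no overlap: 1.84 + 1.49 = 3.3.
- At half these rates: 0.5 to 1.7.

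The neutrophil range starts at day 1, so some of the earlier half could fall in Cycle 1, where the printed step is already 100 mg/m2. The low end could then approach the platelet figure of 0.75.

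**5. Dose difference.** Per course: 5 × 150 = 750 against 5 × 100 = 500 mg/m2. Over Cycles 2-3: 1,500 against 1,000 mg/m2.

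**The case against.** **The rule can be read sensibly.** The rows of Table 9.7.2.b carry a dosing schedule, so they can be taken as courses. An event from the Cycle 1 course then leads to 100 mg/m2 whenever it is seen. This reading is reasonable and would remove the case in step 3, but the text does not state it, and it does not help the unescalated patient in step 2. One could place that patient at Level -1 already and go to Level -2, but Table 9.7.2a prints 150 for the first Cycle 2 event and keeps 100 for a recurrence.

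**There are safeguards.** Section 9.6 calls the parameters a guide, keeps clinical judgment above them, bases changes on the worst preceding toxicity and asks for consultation with the Medical Monitor and the Sponsor. A careful clinician would probably choose 100 mg/m2. This stands as mitigation, but it means overriding a printed number, and Section 9.6 does not supply the step. Nor is 150 always empty: if counts have recovered to the escalation thresholds, it blocks a rise to 200 mg/m2.

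**Stronger readings that the documents do not support:**

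- *Every severe event in Cycle 2 is affected.* From C2D9 an escalated patient has received 200 mg/m2, and 150 is a true reduction.
- *A patient who passes on Day 29 but has grade 2 neutropenia on C2D8 would still get 200 mg/m2.* Section 10.2 does say "Patients will return to the clinic on Day 29 (C2D1) and Day 57 (C3D1) for evaluation", and Section 9.7.2 names no count day. But before C2D9 the current dose is 150 mg/m2, so proceeding at the current dose gives 150, and a count is scheduled on C2D8. The missing count day needs clarifying; it does not show an overdose.
- *Temozolomide moves to days 1-5 in later cycles.* "The dose remains at 200 mg/m2 per day for the first 5 days of each subsequent cycle except if toxicity occurs" reads that way, but days 9-13 stands in the synopsis, Sections 4.6, 5 and 9, Table 9.7.2.b and the calendars. This is carried-over wording.

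**Conclusion.** The concern holds in a limited form. For a patient not escalated at Cycle 2, the printed first step is no reduction on either way of assigning events. For a Cycle 1-course event first seen on C2D1-D8, it is no reduction only if the cycle is read by calendar.

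For this second group the expected number is about 0.9 to 3.3 of 26 patients, or 0.5 to 1.7 at half the Section 7.1 rates; prior tolerance of temozolomide is an entry criterion, so lower rates are plausible. The range assumes that those rates apply here and that nadirs are counted with the first dose as day 1. Counted from the last dose, the number is smaller. The nadir days come from refractory anaplastic astrocytoma. Grade 3 events would add to the number, and patients not recovered within 14 days, who are withdrawn, would reduce it. Unescalated patients with later events are not estimated.

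A reader might extend the dose difference over Cycles 2-6: 3,750 against 2,500 mg/m2. That is a ceiling: it assumes that the optional Cycles 4-6 are given and that no second event occurs.

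The change should be made because it is cheap and bears on safety, not because many patients are at risk.

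**What to change.** 1. In both rows of Table 9.7.2a, replace the cycle-based steps with: *reduce by one step from the dose of the course that preceded the event: 200 to 150, 150 to 100 mg/m2.*
2. Add: *a grade 3-4 cytopenia from the Cycle 1 course, including one first seen on Cycle 2 days 1-8, means no escalation and 100 mg/m2 from Cycle 2.*
3. As clarifications only: state that escalation uses the last CBC before the first Cycle 2 temozolomide dose (C2D8 as scheduled), and give the dosing days of later cycles as days 9-13.

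The cost is wording in Section 9.7.2, with no new visit or test. Steps for patients escalated to 200 mg/m2, and for events seen in Cycle 1, do not change. The one downside is that a patient moved from 150 to 100 mg/m2 is then at the lowest dose, where a recurrence means withdrawal.
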